### **Outcome measures**

#### Pilot outcomes

For this pilot trial, the primary outcome is assessment of criteria for progression to phase III RCT according to the following criteria:

| Criterion number | Red/amber/green criteria  |  |  |
|------------------|---|--|--|
|                  | Red*   | Amber**   | Green***  |
| 1.               | Recruitment and randomisation do not occur within the allocated timescales  | Recruitment and randomisation occur within the allocated timescales  | Recruitment and randomisation occur within the allocated timescales  |
| 2.               | <4 schools are retained in study  | 4 schools are retained in study  | ≥5 schools are retained in study   |
| 3.               | Intervention is implemented with <70% fidelity in ≥2 schools retained in intervention arm                                       | Intervention is implemented with <70% fidelity in 1 school retained in the intervention arm  | Intervention is implemented with ≥70% fidelity in all schools retained in the intervention arm                                       |
| 4.               | Intervention is acceptable to <70% of teachers and students responding to the survey in ≥2 schools retained in intervention arm | Intervention is acceptable to <70% of teachers and/or students responding to the survey in 1 school retained in the intervention arm | Intervention is acceptable to ≥70% of teachers and students responding to the survey in all schools retained in the intervention arm |
| 5.               | Student response rates and completion of outcome measures are   | Student response rates and completion of outcome measures are  | Student response rates and completion of outcome measures are  |

|    | <80% in ≥3 schools retained in the study   | <80% in 1-2 schools retained in the study   | ≥80% in all schools retained in the study   |
|----|--|---|---|
| 6. | Staff response rates and completion of outcome measures are <70% in ≥3 schools retained in the study | Staff response rates and completion of outcome measures are <70% in 1-2 schools retained in the study | Staff response rates and completion of outcome measures are ≥70% in all schools retained in the study |
| 7. | There is evidence of substantial contamination between arms  | There is evidence of some contamination between arms  | There is no evidence of any contamination between arms  |

\* Any red criteria indicate that the study will not progress to a phase III trial.

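### Progression criterion 4 is not exhaustive: if only one of teachers or students falls below 70% acceptability in two or more intervention schools, the result is neither red, amber nor green

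*Protocol*

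**What the plan says.** The Protocol makes assessment of the progression criteria the pilot's primary outcome (Design overview; Pilot outcomes). The notes to the table say that any red means no progression to phase III, that amber may allow a funding proposal if mitigation is found, and that green supports one.

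Criterion 4 (acceptability) reads:

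- Red: "Intervention is acceptable to <70% of teachers and students responding to the survey in ≥2 schools retained in intervention arm".
- Amber: "Intervention is acceptable to <70% of teachers and/or students responding to the survey in 1 school retained in the intervention arm".
- Green: "Intervention is acceptable to ≥70% of teachers and students responding to the survey in all schools retained in the intervention arm".

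Criteria 5 and 6 each join two components in all three columns. Criterion 5 begins "Student response rates and completion of outcome measures are" and continues "<80% in ≥3 schools retained in the study" for red, "<80% in 1-2 schools retained in the study" for amber and "≥80% in all schools retained in the study" for green. Criterion 6 red is "Staff response rates and completion of outcome measures are <70% in ≥3 schools retained in the study", and its amber and green cells follow the same form.

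The text after the table leaves the exact fidelity and acceptability metrics to phase 1. It gives the funder the judgement on whether the criteria are met, informed by the steering committee. It has no rule for a result that fits no column.

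**The concern.** Within one row, red joins the two groups by *and* while amber joins them by *and/or*. On the ordinary reading, red needs both groups to fall short in the same school, in at least two schools, and amber needs only one group to fall short, in a single school. Nothing covers one group falling short in two, three or four schools.

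Research question 2 asks whether progression is justified on pre-specified criteria. For this class of results the protocol does not pre-specify whether the programme stops (red) or may go on with mitigation (amber). Someone would have to decide with the data in view.

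**Working it through.** **Inputs.** There are four intervention schools (Design overview). The cut-off is 70% for each of two groups, and the red, amber and green wording is as quoted. The protocol gives no figure to reproduce here, because this is a decision table.

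**Set-up.** For each school record whether teachers are below 70% and whether students are below 70%. Let A be the number of schools where at least one group is below, and B the number where both are below. As worded:

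- red: B ≥ 2
- amber: A = 1
- green: A = 0
- unclassified: A ≥ 2 and B ≤ 1

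**Example.** Students are below 70% in all four schools and teachers at or above 70% in all four. Then A = 4 and B = 0, so the result is unclassified. With the same shortfall in one school, A = 1 and the result is amber.

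**Pattern count, four schools.** Each school has 4 states, so there are 4^4 = 256 patterns.

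- Green: 1.
- Amber: 4 × 3 = 12.
- A ≥ 2: 256 − 1 − 12 = 243.
- Red (B ≥ 2): 6 × 9 + 4 × 3 + 1 = 67.
- Unclassified: 243 − 67 = 176.

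Of these 176, 4 × 3 = 12 have students short in one school and teachers in a different one. In the other 164, at least one group is short in two or more schools. With three schools retained, 44 of 64 patterns are unclassified; with two, 8 of 16. These are counts of logical patterns, not probabilities.

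**With and/or in red.** Red becomes A ≥ 2. The split is 243 red, 12 amber, 1 green and 0 unclassified.

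**Illustrative probability.** The protocol gives no failure rates. Assume each group falls below 70% in a school with probability p, independently between groups and schools. Then a = 1 − (1 − p)² is the chance that at least one group is short, and b = p² that both are. For x = a or b, P(≥2 of 4 schools) = 1 − (1 − x)^4 − 4x(1 − x)^3. The unclassified probability is the value at a minus the value at b.

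| p | a | b | P(A ≥ 2) | P(B ≥ 2) | Unclassified |
|---|---|---|---|---|---|
| 5% | 0.0975 | 0.0025 | 0.050 | <0.001 | about 5% |
| 10% | 0.19 | 0.01 | 0.166 | 0.001 | about 16.5% |
| 20% | 0.36 | 0.04 | 0.455 | 0.009 | about 45% |

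If teachers and students tend to fall short in the same schools, the unclassified share is lower. If they always do so together, it is zero.

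**Criteria 5 and 6.** There are six schools and two components, so 4^6 = 4096 patterns. If the components must both fall short in a school, the unclassified patterns are those with some shortfall but no school short on both: 3^6 − 1 = 728. If either is enough, none is unclassified. The wording does not settle which reading applies.

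**The case against.** Several points on the other side deserve weight.

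- **Other readings of criterion 4.** Teachers and students might be pooled into one percentage, or amber's one school might mean at least one. Pooling does not fit amber's and/or, which treats the groups separately. Reading amber as at least one school conflicts with the split between 1 and ≥2 schools, and would leave a student shortfall in every school at amber.
- **Human judgement.** The funder decides, informed by the steering committee, and an unclassified result cannot be green. A reader might infer that a worse result earns a milder label. The documents do not support that: no label is not a milder label. What remains is discretion between amber and red after the data are in.
- **Deferral to phase 1.** Only the metrics are deferred. How the two groups combine is not mentioned.
- **Student shortfall everywhere.** A reader might infer that student shortfall in all schools always escapes the table. It does not: if teachers are also below 70% in two or more of those schools, red applies.
- **Criteria 5 and 6.** A reader might infer the same definite gap there. These rows have no contrast between *and* and *and/or*, so they can fairly be read as failing when either component falls short, and then there is no gap.
- **Size.** A reader might take 45% as the share of outcomes left without a category. That figure needs an assumed 20% failure rate and independence, neither of which is in the protocol.

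The objection stands on scope and size. It does not remove the gap in criterion 4.

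**Conclusion.** Criterion 4 as written does not classify every result. The gap follows from the wording alone and needs no assumed rates: one group below 70% in two or more intervention schools is neither red, amber nor green, unless both groups are below together in at least two of them. By pattern count it covers 176 of 256 combinations with four schools. Any probability is illustrative, about 5% to 45% over the assumed rates of 5% to 20%, and lower with positive correlation between the groups.

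Criterion 3 uses the same 0, 1, ≥2 school split without a gap, which suggests a drafting slip in criterion 4. The pilot tests no intervention effects, so the consequence is confined to the progression decision. That decision is the pilot's primary outcome, so the row should be corrected. Criteria 5 and 6 need clarification only.

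**What to change.** Before the May-July 2025 follow-up, with sign-off from the steering and data monitoring committees (which approved the red/amber/green system at version 1.3):

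- **Criterion 4.** Change red to <70% of teachers and/or <70% of students in ≥2 retained intervention schools. This matches amber's wording and criterion 3's split, and makes the three levels exhaustive and mutually exclusive. If the steering committee meant a one-group shortfall in ≥2 schools to be amber, extend amber explicitly instead. The document does not show which was intended.
- **Criteria 5 and 6.** In red and amber, state that response rate and/or completion below the threshold is enough. Green still requires both components.

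The drafting cost is a few words in the table plus the approvals. The substantive cost of the red wording for criterion 4 is that red, which stops progression, becomes materially easier to trigger than on the literal text: 243 rather than 67 of the 256 patterns or, under the illustrative 20% assumption, 45.5% rather than 0.9%. The committees should accept that knowingly, or choose the amber extension.

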#### Trial outcomes to be piloted

The twin primary outcome measures for a future phase III RCT to be assessed for completion in the pilot are binary measures of student-reported bullying victimisation and perpetration in the past 2 months (Revised Olweus Bully/Victim Questionnaire), which have previously been used in existing trials including students age 6-11 with strong reliability/validity.

Secondary student-level outcomes will be:

- teacher-reported social and emotional problems for each student (Strengths and Difficulties Questionnaire total difficulties score);
- student reported cyber-bullying victimisation (DAPHNE measure);
- student-reported wellbeing at school (Adapted How I Feel About My School questionnaire); and
- student attendance/attainment (routine data).

All student-reported measures are suitable for students in the age range being examined here. They will be collected via paper surveys in schools (see below). The pilot RCT will assess the feasibility of collecting teacher-reported data on each student's social and emotional problems by surveying children's classroom teachers using the teacher-completed SDQ.

Secondary teacher-level outcomes will be:

- perceived behaviour of students in their class (Pupil Behaviour Questionnaire);
- self-efficacy (Teacher Sense of Efficacy scale); and
- burnout (Maslach Burnout Inventory).

Economic analysis will include the above outcomes (cost-consequence analyses) and the Child Health Utility (CHU) 9D measure (cost-utility analysis) which was developed using children's input and is validated for use in this age range.

### ***Assessment and follow up***

Baseline surveys will be done before randomisation with students in years 3-6 (age 7-11) and their class teachers in May-July 2024 and will collect data on socio-demographic characteristics, baseline values of outcomes and other covariates, drawing on existing survey items. Consent procedures are described under ethics below.

For students, paper questionnaires will be completed confidentially by students supervised by trained fieldworkers. In the adaptation phase, we will consult with teachers to determine the most appropriate means of surveying students of different ages: either in whole classes, smaller groups or individually. Whichever method is chosen, fieldworkers will read out questions and responses options to students with students then completing their answers. Students will be asked to skip questions they do not understand or do not wish to answer. Students will be advised to contact their school safeguarding lead or other trust staff-member for support should they feel confused or upset as a result of completing the questionnaire, with the team briefing safeguarding leads about this and liaising with them to record where this has occurred. Previous experience indicates that paper questionnaires are acceptable and logistically more straightforward than tablet surveys. We will survey absent students by leaving questionnaires and stamped addressed envelopes with schools, and liaising with schools to maximise returns.

For teacher surveys, we will consult with schools in the adaptation phase to identify the most feasible means of achieving a high response rate. We will then pilot this approach in the pilot RCT phase. We anticipate that the most feasible method for teachers will be to conduct paper-based surveys face to face in specific sessions in school staff rooms.

We will conduct follow-up surveys of students and their teachers at 12 months (May-July 2025). This period is sufficient to assess the feasibility of follow-up in the next academic year after baselines but is not intended to assess impacts of the intervention in this pilot RCT. In a phase III RCT, we would undertake follow-up surveys with students in years 3-6 and teachers at 36 months post-baseline, the likely time required to generate outcomes according to the original Learning Together trial and other research on whole-school interventions. Survey fieldworkers but not students or teachers will be blind to allocation.

### ***Process evaluation data collection***

In addition to assessing progression criteria and informed by existing frameworks, we will examine: levels of intervention fidelity, reach and acceptability and how these vary between schools and students; what is usual treatment in control schools and potential contamination between arms; and implementation processes and intervention mechanisms and how these vary between schools/students.

### ***Intervention fidelity, reach, acceptability and context***

Fidelity of implementation of all intervention components by schools as well as preparatory training will be assessed quantitatively using bespoke measures developed in phase 1 and informed by measures used in the original Learning Together trial. Data will be collected via: audio-recording of all training for school staff; surveys of all school staff undergoing training; logbooks of all school staff implementing action groups and restorative practice

(plus the curriculum if this is delivered as part of the pilot); and structured researcher observations of one randomly selected action group (and curriculum lesson if delivered) meeting per school. Observations will act as a check on the reliability of data from log-books. Restorative practice sessions will not be observed for logistic (they will generally occur at short notice) and sensitivity reasons. We will primarily assess fidelity of form (i.e. of the activities as planned) but, where local adaptations are made, we will assess whether these are consistent or not with the intervention theory of change in order to provide a qualitative assessment of fidelity of function (i.e. alignment of implementation with the theory of change). We will examine reach and acceptability to staff, students (overall and by student gender, ethnicity and free school meal entitlement), and by school-level Ofsted rating and free school meals entitlement. Reach and acceptability will be assessed quantitatively via questionnaire survey items at follow-up.

#### Comparator and potential contamination

We will undertake a structured interview with one staff-member (informed by questions from the School Health Research Network Questionnaire) per control school and draw on student and staff surveys to assess treatment as usual in terms of behaviour management, bullying prevention and mental health provision. The individual sampled will be a member of the senior leadership team with an overview of these areas of provision. We will examine the potential for contamination across arms to assess whether this is a threat to internal validity. We will collect qualitative data to explore implementation and mechanisms, and how these vary between schools and students.

#### Implementation processes/intervention mechanisms and context

Informed by May's implementation theory and realist evaluation, we will collect qualitative data and analyse these in order to explore implementation processes and intervention mechanisms, and how these vary between schools and students. Informed by 'dark logic' methods, we will explore whether any hypothesised mechanisms of harm appear plausible. Data will be collected from intervention schools via: interview with one staff-member and one parent per school, and focus groups with 4-8 staff (purposive by seniority and role) and 4-8 students per school (purposive by involvement in intervention activities, ethnicity and gender) per school. We will also interview staff from Place2Be and L30 Relational Systems. It will not be feasible in schools to purposively sample by student socio-economic status but we will strive to be inclusive of a diverse range of students. Purposive sampling will be used to explore a range of perspectives and experiences according to factors likely to be associated with differences in these.

#### Economic evaluation data collection

The pilot RCT will examine whether it is feasible to assess cost effectiveness using cost-consequence and cost-utility analyses within a phase III trial. The use of CHU-9D is described above. We will assess the feasibility of estimating costs within the trial period arising from primary and secondary outcomes. Within the pilot, study methods to measure the incremental cost of the intervention in a phase-III trial study will be developed and piloted. With use of a broad public and third-sector perspective, resources to be measured will include: resources used by trainers, Place2Be and schools. Within this, key interventional resources will include Place2Be, L30 Relational Systems and school staff time, training events, meetings and consumables. Measures will include: standardised sessional checklists to monitor and document attendance, preparation and delivery time for key training events, action group meetings and restorative practice meetings (as well as the curriculum if this is part of the intervention); and the completion of surveys and log-books by school staff charged with intervention delivery, assessing time spent on tasks relating to intervention, staff travel and other expenses relating to the intervention charged to a specific project grant code.

#### **Data management**

Anonymised linked student and teacher survey data will be managed by LSHTM's accredited CTU with linkage to unique identifier codes (not names) in password-protected files on drives accessible only by named CTU staff. The (institutionally separate) fieldwork team will manage a separate data-file linking names to unique identifiers, in similarly protected files and drives, and will not have access to self-report survey data. This will maintain separation of identifiers and self-report data. Audio-recordings made during the qualitative research will use secure password-protected recorders. These will be transcribed in full by LSHTM-approved contractors with secure data transfer and management processes. Transcripts will be anonymised and stored in secure files and drives by the fieldwork team. All reporting will be fully anonymised to prevent explicit or implicit identification. In line with MRC guidance on personal information in medical research, we will retain all anonymised research data for 20 years after the end of the study. This is to allow secondary analyses and further research to take place, and to allow any queries or concerns about the conduct of the study to be addressed.

## **Data analysis**

### Adaptation phase

Most activities in the adaptation phase will be PPIE rather than research. Such activities will be summarised but not subject to research analysis. The review of reviews will present a narrative summary of evidence pertinent to adapting the Learning Together intervention to primary schools, including any evidence of potential harms and how these might be mitigated. Research data from the survey of schools in south-east England will be analysed to descriptively summarise need for, and feasibility and acceptability of the intervention and its components, including whether a curriculum component should be included.

We will report to the study steering committee and NIHR on whether we recommend that the study should progress to phase 2 based on whether the intervention has been finalised to the satisfaction of the two participating schools, and whether the fidelity and acceptability metrics for the pilot phase have been defined (RQ1). The adaptation phase will also make recommendations as to how best to survey teachers.

### Pilot RCT

Our main analyses will determine whether criteria for progression to a phase III trial are met (RQ2). School randomisation and retention, and survey response rates will be described using a CONSORT diagram. Descriptive statistics on fidelity will draw on audio-recordings of training, log-books of providers and structured observations of action groups (and curriculum lessons if included). Statistics on acceptability will draw on surveys of students and staff. Qualitative data will be analysed to describe relevant activities in and around intervention and control schools; and assess evidence of contamination.

Other analyses will address our other research questions. We will assess the reliability of scaled outcome measures by reporting Cronbach's alpha statistics (RQ3). Descriptive summaries of baseline and follow-up data by arm will be tabulated, reporting completion rates by measure (RQ3-5). We will determine which methods are most feasible to survey teachers (RQ4).

Qualitative data will be subject to thematic content analysis (in vivo/axial codes; constant comparison) informed by May's implementation theory, realist approaches to evaluation and dark logic methods to examine: how contextual factors including school type influence implementation and mechanisms, and refine our theory of change (RQ6); and examine potential mechanisms of action and of harm (RQ7). Qualitative research will describe treatment as usual in control schools (RQ8). Our economic feasibility study will pilot collection of CHU-9D and cost data, and assess the feasibility of methods to be used within a full trial to conduct cost-consequence and cost-utility analyses (RQ9).

A future phase III RCT would undertake intention-to-treat analyses to assess intervention effects on our primary and secondary outcome measures. Additional, secondary analyses would examine on-treatment effects according to school-level fidelity, as well as examine moderation of intervention effects by school-level (free school meals rates, Ofsted rating), student-level (gender, ethnicity, socio-economic disadvantage and school engagement) and teacher-level (gender, role) characteristics. Alongside insights from the process evaluation of how context influenced implementation and receipt, such analyses would provide empirical evidence about the potential transferability of the intervention to different schools and its relevance to addressing different student needs.

